# Phase II:

Two hundred eighty fathers, the female *coparent of their youngest child*, and their youngest biological child aged 9 months to 12 years will participate for a total of up to 840 participants in this Phase 2 randomized controlled efficacy trial.

# Initial screen:

Referred fathers will be asked to complete an initial brief screening if they are interested in participation in the study, which will include demographic matching information such as age, ethnicity, city of residence, income, employment history, substance abuse history etc. He will be told that his screening questionnaire will be reviewed, and he will be contacted to set up further assessment sessions if he is found to be eligible. This will provide the opportunity for contact with the mother to conduct phone screening with her related to IPV and assess her willingness for herself and their shared child to participate.

Fathers will be told that their female co-parents (and if different current intimate partners of more than 6 months) will be contacted but they will not be told when (day or time) this will occur. Female co-parent contact information will be provided on the referral from DCF so that fathers are not providing this information, and this will limit the possibility of coercion. The phone screening with female co-parents will include IPV specific questions (e.g. severity of IPV and status of protective orders). If the father is not eligible based on screening due to severe IPV that involves admitted hospitalization or strangulation, or a current full protective order related to his child, he will be informed that he does not meet our demographic criteria based on his initial screening. No mention of contact with mother will be made. If the father agrees to the study and he is eligible following screening of his female co-parent and she agrees to participate to provide information about their shared child, he will schedule a time to complete the second assessment with the child. Fathers will be able to participate even if their co-parent refuses participation of their shared child as long as he meets other eligibility criteria (no severe IPV involving hospitalization, no full contact protective order with child, mother consents to participate in providing symptom

information about their shared child) to ensure there is no coercion or retaliation toward female co-parents for their decisions about child participation.

#### **Baseline assessments:**

Each father who agrees to participate based on recruitment screening described above will be invited to a 2-hour baseline interview either in person or via a password protected Zoom meeting to ensure security. He will complete standardized questionnaires in interview format with a trained research assistant to assess (a) history and severity of IPV, (b) psychiatric symptoms, (c) self-reported emotion dysregulation, (d) adverse childhood experiences (e) substance use (g) relationship status with the coparent and frequency of contact with his children and (g) reflective functioning (RF). We have successfully used all the included measures in prior studies with the target population without any adverse events.

Fathers will also be asked to attend a second appointment with their child for a structured play assessment. These will take place at [name], New Havenor [name] following all safety protocols outlined by Yale will be followed regarding COVID-19 precautions or via a zoom video conference if in person is not feasible. The father-child play session takes 25 minutes and child questionnaires administered to youth 7 and older will take less than 20 minutes...Mothers will be contacted before for consent for participation of their child and as collateral informants on study assessments. If indicated, current female partners will also be invited as collateral informants. Mothers and female intimate partners may complete study questionnaires via telephone, zoom, or secure online survey link via the Yale Research Electronic Data Capture (REDCap).

The second session with the father will include the target child and include self-report measures of symptoms for children aged 7 and up followed by free play session with their father. This portion will be video recorded with the father and the target child. Fathers will be asked to play with their children for 15 minutes with a set of age appropriate toys. Upon completion of the play time they will be instructed to have their child clean up the toys. These interactions will be video-recorded either at the study offices or via the Zoom secure platform and coded by trained blind, RAs using the Child Interactive Behavior Rating Scale. The scale has age specific coding criteria for infants, toddlers, preschool, and school aged children.

The RA will complete study assessments in person or via zoom with fathers, mothers and partners at baseline, immediately following intervention completion, at 6 and 12 month follow-ups. Each measure and timing of assessment are outlined in Table 1.

Table 1. Assessment	Rater	Baseline	Weekly During	Monthly During	Post- intervention	6& 12 Month- FU
Schedule			Intervention	Intervention		_
ir v Out comes						
Family Socialization Interview Revised (FSI-R)  – IPV module	Masked Coder	X			X	Х
Time-line follow-back for IPV (56, 57)	Father, Mother, Current Intimate Partner		Х			
Abusive Behavior Inventory (ABI)	Father, Mother, Current Intimate Partner	X			X	X
Court and Arrest Records	N/A	X				Х
Child Maltreatment and Parenting Outcomes						
Child Protective Services Records	N/A	X				X
Family Socialization Interview Revised (FSI-R)  – Parenting Risk module	Masked Coder	x			X	X
Timeline Followback-CM Risk	Father and Mother		х			
Conflict Tactics Scale-Parent Child	Father and Mother	x			x	X
Father-Child Free Play coded using Child Interactive Behavior Rating (CIB)+	Masked Coders	X			X	X (12 month only)
Children's Emotions Scale (RCES)	Mother and Father					
Brief Infant Toddler Social Emotional Assessment (BITSEA) Trauma Symptom Checklist for Young Children (TSCYC) or Trauma symptom checklist for children (TSCC) appropriate for child age	Mother and Father Children >7-Self Report	X			X	X
Kiddie Diagnostic Interview Schedule PTSD Module OR Diagnostic Infant and Preschool Assessment (DIPA) modified PTSD module	Mother and Father	X			x	x
Satisfaction Outcomes						
Client Satisfaction Questionnaire 8 (58)	Father				Х	
Intervention Targets (Mechanisms)						
Unified Protocol Skill Use Scale (UPSUS)122 and select items from the 28-item Brief COPE	Father		X			
Difficulties in Emotion Regulation Scale (59) DERS Short Form	Father	X	Х		x	Х
Reflective Functioning Questionnaire-8 (RFQ)(60)	Father	X	Х			
Parent Reflective Function Questionnaire (PRFQ) (61)	Father	X	X			
Intervention Process Variables						
Working Alliance Inventory (62)	Father and Clinician			Х		
CHANGE Coding	Trained Reliable Coders			Х		
Motivation to Change	Father			Х		

	1			1	1
Therapist Session Report Form	Clinician		x		
Other variables to classify the sample					
STRESS Trauma History and PTSD Scale	Father	Х			
Alcohol Use Disorders identification Test (AUDIT) – Self report(66)	Father	Х			
Drug Abuse Screening Test- 10 (DAST- 10)(67)	Father	Х			
TimeLine Follow Back-Substance Use	Father		X		Х
Father Contact and Engagement Scale(68, 69)	Father and Mother	Х		X	х
Brief Symptom Inventory (BSI) (70)	Father and Mother	Х		Х	
CoParent Relationship Scale Children's Exposure to Violence Only	Father and Mother	Х		Х	Х

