# Aims for Phase I:

- 1. Develop a revised BIP manual for individual treatment delivery as a comparison treatment.
- 2. Develop a fidelity measure to distinguish F4C from BIP for therapist fidelity coding.
- 3. Establish acceptability and feasibility of F4C compared to traditional group BIP (BIP-G) and an individually delivered BIP (developed in aim 1 above; BIP-I). We will test the following specific research hypotheses:
  - i. Fathers randomized to F4C will have higher completion rates than those in either the BIP-I or BIP-G treatments.
  - ii. Fathers will report greater working alliance and satisfaction with F4C than either BIP condition
- 4. Assess initial intervention signal of F4C compared with BIP-I (developed in aim 1 above) and a group format BIP-G (current standard of care) program of comparable length. We will test the following specific research hypotheses:
  - i. Fathers receiving F4C will evidence greater improvement in reflective functioning (RF) and emotion regulation post-intervention compared to fathers receiving BIP-I or BIP-G.
  - ii. Fathers receiving F4C will show greater reductions in intimate partner violence (IPV) and child maltreatment (CM) over the 18 weeks of treatment compared to fathers receiving either BIP condition.
  - iii. Fathers receiving F4C will maintain reductions in IPV and CM in the 3 months following treatment.

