Eighteen percent of children in the United States witness Intimate Partner Violence (IPV) in their homes with significant immediate and long-term consequences to physical and psychological health. Exposure to IPV perpetrated by fathers is common among children referred to child protective services with both national and state level data indicating between 30-40% of child welfare reported children are exposed to IPV, which is most often perpetrated by a father figure. Child protective service systems have long focused on mothers in their interventions for both safety and treatment of IPV. Mothers have been tasked with protecting their children from witnessing IPV or risk losing their children.  Further, all the treatment requirements and opportunities are provided to and expected to be carried out by mothers. Fathers are not held accountable nor are they expected to participate in treatments often due to a belief that interventions do not work for this population. This belief comes from several metaanalyses that report near zero effect sizes of current batterer group intervention programs (BIPs). the only broadly available treatment for IPV perpetrators, in reducing violence. Beyond negligible effects, attrition rates, even for court-mandated programs, are high (30-60%) indicating a significant service need. Importantly, even among intervention completers, recidivism rates for BIPs can be 20-30% indicating high intervention failure.  Often, men who continue to use violence following completion of a group BIP are re-referred to the same program or another similar group program of greater length. Others may serve a short jail sentence with no other treatment provided. Families with IPV are frequently involved with child protective services because it is well known that exposure to IPV is detrimental to children and increases their risk for psychosocial and psychiatric difficulties. (12-14) Despite their ineffectiveness child protective services and the courts in many states continue to use completion of BIPs as sufficient to grant child visitation or as evidence that child protective oversight is no longer needed (15, 16)

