# Preliminary Studies F4C development.

First, F4C was developed and piloted by the PI in an outpatient clinic setting. A sample of 10 fathers were referred by child protection and the courts to participate in an open trial of initial feasibility. Completion rates were 80% and all fathers who completed the program remained non-violent during treatment with very high satisfaction indicating good potential for intervention acceptability. Next, using content, treatment manuals, and training materials developed during the pilot study outlined above, [name] trained 12 clinicians in

community mental health clinics to deliver F4C to child protection involved families through a statewide initiative in CT. Based on session fidelity reviews it is clear clinicians have successfully implemented the intervention using the manual and training curriculum. Based on a sample of 73 fathers referred to F4C, 74% completed the program. Importantly 68% of those referred to F4C had previously participated in a BIP. Additionally, fathers self-reported significant improvements

in the intervention targets of emotion regulation and reflective functioning from pre to post intervention (p<.05). There were significant reductions in IPV post-intervention based on mothers and fathers reports (see Figure 2) and significant reductions in child maltreatment risk based on the Parental Acceptance Rejection Questionnaire (t (67) = 6.44, p < .00) These data support F4C's ability to improve hypothesized intervention targets and IPV and child maltreatment outcomes. The current study is needed to provide an initial randomized test of F4C compared to an individually delivered BIP and group BIP. The randomized three group study will allow us to test F4C compared to BIP-I and Group BIP (BIP-G) and indicate whether the individual treatment format is the driving factor OR the content OR both.

3. **Research Plan:** Summarize the study design and research procedures using non-technical language that can be readily understood by someone outside the discipline. If working with a Non-Government Organization (NGO) or other organization, be sure to highlight which are research-only activities and which activities would occur regardless of the research. If working with survey firms, please specify what research activities the research firm will be responsible for.

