# Treatment Phase.

Each treatment will be delivered weekly over 18 weeks. Male participants will meet online or be contacted via phone weekly with the RA to complete self-report assessments of IPV behaviors, father-child interactions and *substance use*. The RAs will be blind to the participants' treatment conditions. Study therapists will complete weekly session reports of session content and skill acquisitions based on completed homework.

*Fathers for Change*: F4C focuses on: 1) the fathering role to facilitate engagement, 2) RF to understand self, partner and children and emotion regulation skills to reduce IPV and child maltreatment F4C focuses on understanding of emotional experiences, how they impact thinking and behaviors related to partners, co-parents and children. F4C clients will meet individually with their F4C therapist for 50 minutes per week over 18 weeks.

**Batterer Intervention Program:** The BIP is a psychoeducational intervention that will be delivered in 50- minute individual sessions over 18 weeks. The intervention focuses on the impact of violence on victims, power and control tactics, and societal influences supporting men's violence toward women. The intervention includes didactics and experiential exercises including role plays to teach management skills. anger BIP is typically delivered in a group format, however will also be adapted to an individual Therapies will be delivered either in person or via format as part of the current study. secure/password protected zoom virtual sessions. All Yale safety protocols with regard to COVID-19 will be followed.

**Therapist Training.** Master's level clinicians will be trained to deliver the study interventions. [name] will utilize the therapist training manual, slides and videos generated from her pilot studies to train F4C therapists. She will meet weekly with F4C therapists for supervision. BIP-I and BIP-G therapists will be trained by [name] using the BIP manual and training materials modified for individual treatment delivery. BIP clinicians will meet weekly with [name] for supervision and intervention adherence.

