# Follow-up:

6 and 12 months post-intervention, fathers and coparents will participate in follow-up interviews to assess IPV, child maltreatment risk, father engagement and parenting. Participants will complete these interviews over zoom or telephone. They will be paid \$50 and mothers \$35.

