# 4. How was this estimate derived?

Phase I: Seventy-five fathers, the female co-parent of their youngest child, and their child will participate for a total of up to 225 participants. We intend to include all 75 fathers assigned to study interventions for intent to treat analysis. The planned sample size of 75 participants who will provide data for inclusion in our intention-to-treat analysis should provide sufficient power to detect clinically meaningful differences between and within treatment conditions as specified in our primary aims. A sample of 63 people provides power of 80% to detect a standardized treatment group differences at 18 weeks of d = 0.45. For purposes of power estimates, we assumed d = 0.45 will represent a potentially meaningful clinical difference in both our primary and mechanism outcomes. In a pilot study examining F4C on participant IPV effect size for outcome was d = 0.86. We will enroll 75 participants to accommodate a 16% loss to follow-up.

Using these procedures in prior studies, our rate of successful follow-up has ranged from 70-90%. With 280 participant families randomized and an aim of at least 70% completion, we expect to have 196 cases with complete treatment and follow-up data.

**4. Process of Consent/Assent** (*NOTE: When a study includes minors, parent provide permission [not consent] for the child's participation, and the child provides assent for participation)* 

Describe the setting and conditions under which consent/assent will be obtained, including parental permission or surrogate permission and the steps taken to ensure participants' independent decision-making.

Fathers will complete informed consent either in person or online via Yale's REDcap data system, in line with guidance on obtaining informed consent during the COVID-19 pandemic. Each will agree to have their female co-parent contacted for consent of participation of their shared child.

Mothers will complete informed consent related to their own participation and the participation of children in which they are the primary guardian. This will be completed online via Yale's REDcap system..

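### Post-treatment and follow-up visits are tied to the end of the intervention, with no date for fathers who stop early or finish late, so assessment timing or missingness could differ by arm

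*Combined protocol and SAP*

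**What the plan says.** Section IV, Baseline assessments, places the assessments "at baseline, immediately following intervention completion, at 6 and 12 month follow-ups". The Follow-up paragraph adds: "6 and 12 months post-intervention, fathers and coparents will participate in follow-up interviews". The Phase I aims use the same kind of anchor over a shorter period: "Fathers receiving F4C will maintain reductions in IPV and CM in the 3 months following treatment". No visit is dated from randomisation and no visit window is given.

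On treatment length, the Treatment Phase text states: "Each treatment will be delivered weekly over 18 weeks". The Phase I sample-size text (Section V, How was this estimate derived?) refers to "standardized treatment group differences at 18 weeks of d = 0.45". The Background description of F4C and the records paragraph in Section VI, item 3, both give 26 weeks instead.

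On completion, a Phase I hypothesis reads: "Fathers randomized to F4C will have higher completion rates than those in either the BIP-I or BIP-G treatments". The preliminary studies report: "Based on a sample of 73 fathers referred to F4C, 74% completed the program". The Background cites 30-60% attrition for existing batterer programmes. For Phase II, Section V sets an overall aim of at least 70% completion, not split by arm.

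On fathers who leave, Section VI, item 2, promises attempts to keep them for intention-to-treat analysis, and Section V includes all 75 Phase I fathers. Neither gives an assessment date. Trial Safety lists events that end a father's participation in the intervention; one is a family-violence incident leading to a no-contact order for the child.

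**The concern.** An assessment date should not depend on something that treatment can change. Here it depends on when, or whether, a father finishes. One who stops halfway has no completion date. He might be seen when he stops, seen at the planned end, or not seen at all, and the protocol does not choose. One whose sessions run over may be seen late. Because a violent incident can itself end the intervention, the anchor can also be moved by the outcome.

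If completion differs between arms, two things could follow. Outcomes could be measured at different average times since randomisation. Or post-treatment data could be missing for reasons tied to the assigned treatment, which would weaken an intention-to-treat comparison.

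The logs share the problem. In Table 1 the follow-back calendars for partner violence and child maltreatment are collected only weekly during the intervention. They feed the Phase I sum score of incidents, for which the Analytic Plan states no exposure time, and they inform the masked ratings on the FSI-R, named as the primary outcome measure. The Aim 1 growth models run across the same visits, yet unequal measurement intervals are discussed only under Aim 2.

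**Working it through.** The plan gives no figure for visit timing, so there is none to reproduce. The one related number agrees with its inputs: 280 × 0.70 = 196 families with complete treatment and follow-up data. That leaves up to 280 − 196 = 84 without. How many of these would be treatment drop-outs is not stated.

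The rest is an illustration.

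Inputs from the documents:
- planned length 18 weeks in both arms (Treatment Phase);
- F4C completion 74% (Preliminary Studies);
- BIP completion 40% to 70%, that is, 100% minus the 30-60% attrition in the Background.

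Assumptions, not in the documents:
- treatment starts at randomisation;
- completers finish at week 18;
- non-completers are assessed at week t, with t = 4, 9 or 14 (seen when they stop) or 18 (seen at the planned end).

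Mean weeks to the post-treatment visit = c × 18 + (1 − c) × t, where c is the completion proportion. The difference between arms is therefore (c for F4C − c for BIP) × (18 − t).

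| BIP completion | t | F4C mean | BIP mean | Difference (weeks) | BIP/F4C |
|---|---|---|---|---|---|
| 70% | 4 | 14.36 | 13.80 | 0.56 | 0.96 |
| 70% | 9 | 15.66 | 15.30 | 0.36 | 0.98 |
| 70% | 14 | 16.96 | 16.80 | 0.16 | 0.99 |
| 40% | 4 | 14.36 | 9.60 | 4.76 | 0.67 |
| 40% | 9 | 15.66 | 12.60 | 3.06 | 0.80 |
| 40% | 14 | 16.96 | 15.60 | 1.36 | 0.92 |
| either | 18 | 18.00 | 18.00 | 0.00 | 1.00 |

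Example: with BIP completion 40% and t = 9, F4C is 0.74 × 18 + 0.26 × 9 = 15.66 and BIP is 0.40 × 18 + 0.60 × 9 = 12.60.

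For the 12-month visit, add 52 weeks to each mean. The BIP/F4C ratio then lies between 61.60/66.36 = 0.93 and 68.80/68.96 = 1.00, so the relative effect is mainly at the post-treatment visit.

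The two stated treatment lengths differ by 26 − 18 = 8 weeks, so the end of the intervention is itself ambiguous by that amount.

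**The case against.** The strongest reply is that both arms have the same planned length and number of sessions, and that the Phase I power statement already speaks of 18 weeks. If staff see drop-outs at the planned end, the windows are equal whatever the completion rates. Research assistants also pursue the weekly log when a session is missed, and Section VIII pays for logs over 18 weeks. All of this stands, and it shows that unequal windows are possible, not inevitable. It does not close the gap: none of these passages says when a father who has left treatment is assessed, or that his logs continue.

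A reader might infer more than the documents support, in four ways.

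- **That the protocol expects unequal completion in Phase II.** The completion hypothesis belongs to Phase I, whereas the 6- and 12-month schedule matches the Phase II aims. For Phase II a difference is only inferred, from an uncontrolled F4C series and from attrition in existing programmes. The Phase II comparator is delivered individually and matched on sessions.
- **That incident counts shrink in proportion to the window**, for example by about 20% at the 0.80 ratio above. No measure is said to be recalled since the last visit, and the FSI-R recall period is not given. The Phase I sum score uses weekly logs and official records, and Table 1 collects neither at the post-treatment visit. The records request names a fixed 26 weeks. Moving the visit alone would not change those counts; the length of log collection after drop-out might.
- **That intention to treat is abandoned.** The protocol states the intention to keep drop-outs; what is missing is the date on which they are assessed.
- **That the design favours F4C.** A shorter BIP window would tend to lower BIP counts and so hide a benefit of F4C. If non-completers are simply missing, the direction is unknown.

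**Conclusion.** The point holds as a weakness in the visit rule. The stated anchor is a post-randomisation event that attendance affects and that an outcome event can cut short, and it has no value for fathers who do not finish. Timing or missingness could therefore differ by arm.

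The documents do not settle how large the effect would be. The range of 0.16 to 4.76 weeks rests on background completion rates carried over to this trial and on an assumed stopping week. The upper end needs the worst BIP completion (40%) together with very early stopping (week 4); at 70% BIP completion the difference stays below 0.6 weeks. It falls to zero if drop-outs are seen at week 18. The effect on the FSI-R cannot be sized. The case for change rests on a better rule being available at little cost, and does not require showing that bias will occur.

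**What to change.** First reconcile the 18-week and 26-week statements of treatment length, so that the planned end is a single number. Then:

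- Date the post-treatment visit at a fixed time from randomisation equal to that planned length, with a stated visit window.
- Date the 6- and 12-month visits at fixed intervals from that same date.
- Apply these dates to every randomised father regardless of attendance, including those who stop, are removed from the intervention or run late.
- Collect the weekly logs, and count child-protection and arrest records, over the same fixed periods in both arms.

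Under the illustration above this sets t to the planned end for everyone, and the difference between arms becomes zero at any pair of completion rates.

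The cost is a scheduling rule and some rewording, plus the effort of reaching fathers who have left treatment, which the protocol already intends to make. The downside is that some fathers with delayed sessions will be assessed before their last session.
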